### **3.3.4.2 Withdrawal of consent to trial participation**

Patients may withdraw their consent to trial participation at any time without the need to justify the decision.

If a patient wants to withdraw consent, the investigator should be involved in the discussion with the patient and explain the difference between trial treatment discontinuation and withdrawal of consent to trial participation, as well as explain the options for continued follow-up after trial treatment discontinuation, please see [section 3.3.4.1](#) above.

### **3.3.4.3 Discontinuation of the trial by the sponsor**

Boehringer Ingelheim reserves the right to discontinue the trial overall or at a particular trial site at any time for the following reasons:

1. Failure to meet expected enrolment goals overall or at a particular trial site.
2. New efficacy or safety information invalidating the earlier positive benefit-risk-assessment, please see section 3.3.4.1.
3. Deviations from GCP, the trial protocol, or the contract impairing the appropriate conduct of the trial.

Further follow up of patients affected will occur as described in [section 3.3.4.1](#).

The investigator / the trial site will be reimbursed for reasonable expenses incurred in case of trial termination (except in case of the third reason).

## **4. TREATMENTS**

### **4.1 INVESTIGATIONAL TREATMENTS**

#### **4.1.1 Identity of the Investigational Medicinal Products**

Table 4.1.1:1                   Test product 1

Substance:	BI 3011441
Pharmaceutical formulation:	Capsules
Source:	Boehringer Ingelheim Pharma GmbH & Co. KG
Unit strength:	0.5mg, 2 mg
Posology:	Once daily
Mode of administration:	Oral

The gelatin used for the manufacture of BI 3011441 soft capsules is manufactured from bovine bones free from skulls, spinal cord, and vertebrae from cattle over 30 months, which does not satisfy risk criteria in Japan for transmissible spongiform encephalopathy. However, appropriate acid process according to the Note for guidance on minimising the risk of transmitting animal spongiform encephalopathy agents via human and veterinary medicinal products (EMA/410/01 rev.3), (2011/C 73/01), from the European Union are used.

#### **4.1.2 Selection of doses in the trial**

A starting dose of 4 mg of BI 3011441 is expected to be a safe starting dose as this is 50% of the MTD, which was identified in Phase 1 study with Caucasian patients. For details please refer to the Investigator's Brochure. Dose escalation steps will be guided by a BLRM. The provisional dose levels to be assigned to separate cohorts of patients are listed in [Table 4.1.2: 1](#). Intermediate or lower dose levels may be investigated, depending on the number of DLTs observed in the trial, as long as they fulfil the EWOC criterion and if agreed upon by the SMC. For dose level 3, proposed dose is 8 mg, but depend on BLRM, 7 mg might be selected. Based on result of dose level 3, further investigation of 7 mg or 8mg will be conducted depend on BLRM.

Table 4.1.2:1 Provisional dose levels for escalation

Dose level	Proposed dose	Increment from previous dose
1	4 mg	Starting dose
2	6 mg	50 %
3-1	7 mg	16.7 %
3-2	8 mg	33.3 % (v.s. 6 mg) 14.3 % (v.s. 7 mg)

At the end of each treatment cohort, BI will convene a meeting with the SMC members. At the dose escalation meeting, the clinical course (safety information including both DLTs and all CTCAE grade  $\geq 2$  toxicity data during the MTD evaluation period) for each patient in the current dose cohort will be described in detail (Including the adverse event information from patient who were excluded from DLT evaluation for reasons other than a DLT). Updated safety data on other ongoing patients, including data beyond the MTD evaluation period, will be discussed as well. Based on that, a decision on the next dose level(s) to be tested is made. Dose escalation will continue until identification of the MTD or RD, safety concerns arise, or the trial is terminated for other reasons.

#### 4.1.3 Method of assigning patients to treatment groups

There will be no randomisation in this trial, as it is a single-arm open-label trial.

Patients will be assigned into escalating dose groups by order of admission into the trial. An interactive response technology (IRT) system is used to register participation of patients in the trial. Upon acquisition of informed consent, study sites access the IRT to register patients for screening. After assessment of all inclusion and exclusion criteria, study sites access the IRT to register each eligible patient for treatment, and the IRT system will assign the patient to the cohort which is open for recruitment.

As soon as the planned number of patients in a cohort are registered for treatment, IRT will close the screening until the next cohort is opened for recruitment or until further treatment slots become available in the current cohort. Patients who are already in screening at the time of the closure of the screening and who then meet all eligibility criteria can be registered for treatment. If more patients are eligible than planned number of patients for a cohort, it is exceptionally allowed to register more patients than planned for ethical reasons

#### 4.1.4 Drug assignment and administration of doses for each patient

Patients will be assigned to their doses based on the available toxicity information (including DLTs, AEs that are not DLTs, and AE information post MTD evaluation period), and anti-tumour activity information, as well as the recommendations from the SMC members following the dose decision meeting, please see [section 4.1.2](#).

#### 4.1.4.1 Administration

The different capsule strengths should not be combined in the same bottle at any time. BI 3011441 capsules must be stored in the containers provided and handled according to the labelled storage instructions and shelf life. Labels will be prepared in accordance with Good Manufacturing Practice (GMP) and local regulatory guidelines.

Patients will be advised to return any unused BI 3011441 in the dispensed bottles, in addition to returning any empty bottles. All patients will be required to complete a patient diary to document BI 3011441 intake, which must be returned to the clinic for review at each clinic visit.

BI 3011441 doses should be taken orally at approximately the same time each morning with the exception of certain trial visit days.

Whenever possible, all doses of BI 3011441 should be taken with water limited to a maximum of 100 mL per capsules and the total amount of water intake should be within the range of 300-500 mL. Capsules should be taken without food, at least 1 hour before a meal or 1 hours after a meal.

For all visits which plan to conduct PK sampling, patients will be asked to fast overnight (minimum of 10 hours) prior to the visit. Pre-dose laboratory samples will be collected prior to receiving the single morning dose.

Missed doses should not be made up if more than 6 hours have passed since scheduled dosing time. Missed doses must be recorded in the patient's diary.

Before initiating a new treatment cycle, all of the following criteria must be met:

- Ophthalmologic exam (if scheduled at the respective cycle visit): No evidence of Retinal Pigment Epithelial Detachment (RPED) or Retinal Vein Occlusion (RVO)
- Echocardiography (if scheduled at the respective cycle visit):
  - No evidence of an absolute decrease in LVEF of 10 percentage points or greater from screening value, to a value that is below institutional lower limit of normal (LLN).
  - No evidence of an absolute decrease in LVEF of 15 percentage points or greater whether below or above institutional LLN, even if the patient is asymptomatic.
- Absence of related clinically significant adverse events: At the planned start of a treatment cycle patients may continue therapy only after recovery to a level which would allow further therapy; i.e. CTCAE Grade 1 or pre-treatment value or considered not clinically significant (except for the following CTCAE Grade 2 AEs: neuropathy, alopecia and fatigue/asthenia).

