- c) Physical examinations including the measurements of height (screening only) and weight will be done at screening, on Day 1 of each treatment cycle, at the end-of-treatment (EOT) visit, at the 30-day end of residual effect (EOR) visit, and at the follow-up (FU) visits for progressive disease. ECOG performance status will be done at screening, on Days 1 and 15 of Cycle 1, Day 1 of Cycle 2, on Day 1 of every other cycle beginning with Cycle 3, at the EOT visit, at EOR, and at FU visits for progressive disease.
- d) A patient diary will be given to the patient for continuous use through the trial. It should be given to the patient at the start of each cycle. The diary collects information about BI 3011441 taken at home and provides reminders about fasting blood samples. After one week on trial medication, treatment compliance should be discussed with the patient, to ensure that the medication is being taken correctly (no compliance calculation has to be performed). Then at Visit 1 of each cycle and at EOT treatment compliance needs to be checked including compliance calculations.
- e) 12-lead electrocardiograms (ECGs) will be done in triplicate before blood work or other procedures after 5 minutes of rest at screening, see [section 5.2.4](#).
- f) LVEF is measured by echocardiography at screening, Day 15 of Cycle 1, C2V1, then every 2 cycles (i.e. C4V1, C6V1, C8V1, etc.) and EOT. Additional LVEF assessments should also be done if clinically indicated.
- g) Safety laboratory assessments including haematology, serum biochemistry, coagulation, pregnancy tests, urinalysis and virology (only at screening) will be performed locally. If screening laboratory tests are completed within 72 hours prior to first dose, predose samples on Day 1 of Cycle 1 will not be repeated. See [Section 5.2.3](#) for further detail. Pregnancy tests are mandatory for women with child-bearing potential. A serum beta human chorionic gonadotropin ( $\beta$ -HCG) pregnancy test must be done at screening. Thereafter, this test can be done in either serum or urine on Day 1 of each cycle, at the EOT visit, and at EOR.
- h) An ophthalmological assessment must be done at screening, C2V1, C3V1, C4V1 and then every 2 cycles (i.e. C6V1, C8V1, C10V1, etc.) and EOT. Ophthalmological assessment can be done separated  $\pm 2$  day from visit. Additional ophthalmological assessments should also be done if clinically indicated.

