### **3.3.4.1 Discontinuation of trial treatment**

An individual patient will discontinue trial treatment if:

- The patient wants to discontinue trial treatment, without the need to justify the decision.
- The patient has repeatedly shown to be non-compliant with important trial procedures and, in the opinion of both, the investigator and sponsor representative, is not willing or able to adhere to the trial requirements in the future.
- The patient needs to take concomitant medication that interferes with the investigational medicinal product or other trial treatment
- The patient becomes pregnant. The patient can no longer receive trial treatment for medical reasons (such as surgery, adverse events or other diseases).

BI 3011441 should be permanently discontinued in case of :

- Retinal vein occlusion (RVO)
- Symptomatic heart failure
- Interstitial lung disease/pneumonitis, regardless of grade
- Recurrent Grade 4 AEs or persistent Grade 2 to 3 AEs that do not recover to Grade 1 or less within 12 weeks
- Drug-related Grade 4 AEs.

An interruption of treatment or delayed start of treatment of more than 4 weeks or several interruptions exceeding a total of  $\geq 28$  days of BI 3011441 treatment due to SAEs/AEs will lead to permanent treatment discontinuation. However in well-justified cases if considered clinically indicated by the Investigator and aligned with the Sponsor (to be documented in writing), a patient can be re exposed to treatment.

In case of a temporary reason, trial treatment should be restarted if medically justified, please see [section 4.1.4](#).

If new efficacy/safety information of BI 3011441 becomes available, Boehringer Ingelheim (BI) will review the benefit-risk-assessment and, if needed, pause or discontinue the trial treatment for all patients or take any other appropriate action to guarantee the safety of the trial patients.

Even if the trial treatment is discontinued, the patients remain in the trial and, given their agreement, will undergo the procedures for early treatment discontinuation and follow-up as outlined in the [Flow Chart](#) and [section 6.2.3](#).

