#### 4.1.4.2 Dose reductions and dose delays

For the assessment of the severity of adverse events (AEs), CTCAE version 5 ([R18-1357](#)) will be used. Any SAEs/AEs of  $\geq$ Grade 2 deemed intolerable by the patient or the treating physician and not responding to appropriate medical management, and any related SAEs/AEs of  $\geq$ Grade 3 will result in the interruption of treatment with BI 3011441 until resolution to baseline or Grade 1. Please see [section 3.3.4.1](#) for the permanent IMP discontinuation criteria.

Proprietary confidential information © 2020 Boehringer Ingelheim International GmbH or one or more of its affiliated companies

If the treatment interruption is  $\leq 2$  weeks, the patient can be re-exposed to BI 3011441 at the same dose or one dose level lower than the dose administered before the interruption as long as the re-exposure is considered clinically indicated by the Investigator. However, dose reduction is not allowed for patient who uses 4 mg, and the study medication (BI 3011441) needs to be discontinued.

In case the treatment is delayed due to an AE, the patient should visit the site at least once a week for assessment of safety laboratory and AEs. More frequent visits may be appropriate as assessed by the Investigator. Any case of a delay in treatment cycle for more than 2 weeks should be communicated to the Sponsor. The Investigator in agreement with the Sponsor will decide about further treatment of individual patient, based on known risk/benefit of BI 3011441.

A maximum of 1 dose reductions of BI 3011441 are allowed, if lower tested dose levels are available. Dose reductions will be only to doses previously explored in earlier cohorts.

In case of dose reductions, all future dose administrations will also be at the reduced dose level. If that is intolerable (as previously described), the treatment of that patient should be discontinued. Recommendations for dose reductions of BI 3011441 are given in [Tables 4.1.4.2: 1, 4.1.4.2: 2, and 4.1.4.2: 3](#).

Proprietary confidential information © 2020 Boehringer Ingelheim International GmbH or one or more of its affiliated companies

Table 4.1.4.2: 1

Dose modification for BI 3011441 for haematologic and non-haematologic toxicity related to treatment

Haematologic and non-haematologic toxicity	Dose modification
Grade 1	

Continue BI 3011441 at full dose, monitor as clinically indicated.

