Grade 2	

Provide appropriate medical management as clinically indicated.

Consider holding BI 3011441 until resolution to Grade 1 or baseline and resume BI 3011441 at the same dose.

Deemed intolerable by the patient or the treating physician in case of continuation of BI 3011441 and not responding to appropriate medical management, interrupt BI 3011441 until resolution to baseline or Grade 1 and then, resume BI 3011441 at the reduced dose by 1 dose level.

Grade 3 a	

Interrupt BI 3011441 until toxicity is Grade 1 or baseline, and then reduce the dose of BI 3011441 by 1 dose level.

The patient may be continued at the same dose if the toxicity is unequivocally considered to be unrelated to BI 3011441 by the Investigator in agreement with the Sponsor.

Continue monitoring as clinically indicated and provide appropriate medical management as needed.

Grade 4 a	

Discontinue BI 3011441.

Continue monitoring as clinically indicated and provide appropriate medical management as needed.

a If the patient has a Grade 3 or 4 laboratory abnormality that, in the judgement of the investigator, is not considered clinically significant, dose modification is not required.

Table 4.1.4.2: 2 Dose modification for retinopathy in BI 3011441

Adverse event	Dose modification
Grade 1	

• Immediately refer to the patient for ophthalmologic exam (if an ophthalmologic exam cannot be performed within 7 days, interrupt BI 3011441).

• If an ophthalmologic exam is done within 7 days and no worsening, continue BI 3011441 and monitor as clinically indicated.

• If retinopathy worsens to Grade 2 or 3, see below for guidance.

Grade 2 or Grade 3	

• Immediately refer to the patient for ophthalmologic exam.

• Interrupt BI 3011441 until resolution to baseline or Grade 1 and then, resume BI 3011441 at the reduced dose by one dose level.

• Continue monitoring as clinically indicated and provide appropriate medical management as needed.

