  - After holding the trial drug and obtaining a follow-up echocardiography within 4 weeks, LVEF has returned within the normal institutional range or to within 5 percentage points of the screening value, but on re-challenge there is second decline of an absolute decrease in LVEF of 10 percentage points or greater from screening value, whether above or below institutional LLN.
- Symptomatic heart failure
- Any retinopathy  $\geq$  Grade 2
- Retinal vein occlusion of any grade.
- Interstitial lung disease/pneumonitis of any grade
- Hepatic injuries assessed as related to trial drug and which meet the AESI criteria for hepatic injury in [Section 5.2.6.1.4](#)
- Treatment pause of BI 3011441 for  $\geq$ 14 days, or dose reduction in Cycle 1 due to treatment-related AEs
- Any treatment-related  $\geq$  Grade 2 toxicity that persists and results in a more than 2 weeks delay of administration of BI 3011441 on Cycle 2 Day 1
- Any treatment-related AE that would require permanent discontinuation of BI 3011441.

Any other toxicity considered significant enough to be qualified as DLT in the opinion of the Investigators, and confirmed by the SMC, will be reported as a DLT.

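### The cycle-start eye criterion in 4.1.4.1 bars a new cycle for any RPED, while the Grade 1 rows of the dose-modification tables continue treatment, and no text says which rule prevails

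*Protocol*

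**What the plan says.** **Cycle start.** Protocol 4.1.4.1 introduces its list with "Before initiating a new treatment cycle, all of the following criteria must be met". The eye item is "Ophthalmologic exam (if scheduled at the respective cycle visit): No evidence of Retinal Pigment Epithelial Detachment (RPED) or Retinal Vein Occlusion (RVO", with no grade. The other two items carry thresholds. The LVEF item uses an absolute fall of 10 points to below the institutional lower limit, or of 15 points at any level. The adverse-event item accepts recovery to Grade 1, to the pre-treatment value, or to a state judged not clinically significant.

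**Action by grade.** In Table 4.1.4.2:2 (retinopathy), the Grade 1 row says "If an ophthalmologic exam is done within 7 days and no worsening, continue BI 3011441 and monitor as clinically indicated". Grade 2 or 3 is interrupted and resumed one dose level lower at baseline or Grade 1. In Table 4.1.4.2:1 (general toxicity), the Grade 1 row says "Continue BI 3011441 at full dose, monitor as clinically indicated".

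**Timing.** Flow Chart footnote h schedules the exam at Visit 1 of Cycles 2, 3 and 4 and then every second cycle. It adds "Ophthalmological assessment can be done separated", within 2 days either side of the visit. Eligibility for the next cycle is a Visit 1 item, and drug intake is daily and continuous.

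**Route to a DLT.** Section 3.3.4.1 says that "An interruption of treatment or delayed start of treatment of more than 4 weeks" because of adverse events leads to permanent discontinuation, with re-exposure possible in well-justified cases agreed with the sponsor. Section 5.2.6.3 lists among the DLTs "Any treatment-related AE that would require permanent discontinuation of BI 3011441", without a grade.

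**The concern.** The two rules give opposite actions for the same finding on the same day, on a risk that the protocol itself names: Table 1.4.2:1 records ocular toxicity in the first-in-human study. Sites that follow different sections would manage identical patients differently. In a trial of about 12 patients, exposure and later DLT status could then depend on which section was read. The eye criterion also cannot be checked before the cycle starts if the exam is done in the later half of its window.

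**Working it through.** The plan gives no figure for this point, so the check is a side-by-side reading followed by a day count.

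**1. Same finding, three instructions.** The documents do not say whether RPED counts as retinopathy, so both tables are shown.

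| Finding at a scheduled cycle-start exam | 4.1.4.1 | Table 4.1.4.2:2 | Table 4.1.4.2:1 |
|---|---|---|---|
| RPED, Grade 1 | Do not start the cycle | Continue, if an exam within 7 days shows no worsening | Continue at full dose |
| RPED still visible, improved from Grade 2 or 3 to Grade 1 | Do not start the cycle | Resume one level lower | Resume, at the same or a reduced dose depending on the row |

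The conflict is present whichever table applies.

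**2. Does other text resolve it?**
- The adverse-event item of 4.1.4.1 accepts Grade 1, but every item in the list must be met, so the eye item still blocks.
- Exclusion criterion 7 bars a history or current evidence of RPED. An on-study RPED should therefore be new, and the tables' reference to baseline does not remove the conflict.
- The LVEF item uses the same falls that trigger interruption at Grade 2 in Table 4.1.4.2:3. The eye item has no matching threshold in its table.
- The RVO half of the eye item raises no such issue. Section 3.3.4.1 discontinues for RVO, and 5.2.6.3 counts it as a DLT at any grade.

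**3. Timing.** If the exam falls 2 days after Visit 1, daily doses on the visit day and on the next day (two doses of the new cycle) precede the exam that is meant to permit them. An exam on or before the visit raises no problem.

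**4. Can a hold caused only by the eye criterion, below Grade 2, become a DLT under 5.2.6.3?**
- Retinopathy criterion: no, it starts at Grade 2.
- Cycle 2 Day 1 delay clause (more than 2 weeks): no, it needs related toxicity of Grade 2 or higher.
- Pause of at least 14 days for related events: no grade floor, but it is unclear whether the words limiting the clause to Cycle 1 apply to the pause or only to the dose reduction.
- Permanent discontinuation: yes, if the event is treatment-related, the hold exceeds 4 weeks and re-exposure is not agreed.

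**5. When would that happen?** Cycle 2 Day 1 is nominally Day 29. A hold covering Days 29 to 56 lasts 28 days, so it exceeds 4 weeks on Day 29 + 28 = Day 57. The visit window of 2 days either side moves this to Day 55 to 59. The MTD evaluation period is the first 28-day cycle (protocol 2.1.1), or first dose + 28 days, that is Day 29 (SAP Table 6.1:1). The event would qualify about 4 weeks after that period closes. Even the 14-day pause, read broadly, would complete only on Day 42 (Days 29 to 42).

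**6. Where would it count?** It would count in the on-treatment DLT secondary endpoint (2.1.3), in the recommended dose (5.2.6.3 uses DLT-type events from all cycles) and in the end-of-escalation rerun with all DLTs (2.1.1).

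**The case against.** The strongest defence is that the rules can be read together. Section 4.1.4.1 is mandatory and specific to cycle starts with a scheduled exam, whereas 4.1.4.2 introduces its tables as recommendations. That reading is reasonable, but the protocol does not state it. Dosing is continuous, so at a cycle-start visit both rules apply on the same day. The reading would also treat a lesion through mid-cycle and hold the same lesion on Day 1.

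Several limits stand. The documents never grade RPED beyond naming CTCAE version 5. Footnote h is permissive, and only its after-visit half conflicts with the criterion. The delay clause already sets a Grade 2 floor for late Cycle 2 starts. Discontinuation after 4 weeks is not automatic, and 4.1.4.2 refers delays beyond 2 weeks to the investigator and the sponsor.

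A reader might go further and infer that the conflict changes the MTD. The documents do not support that, for three reasons:
- Section 5.2.6.3 counts DLTs seen at the Cycle 2 Day 1 eye exam, not every eye finding. A Grade 1 finding there is not a DLT under the retinal criterion.
- By the day count, the discontinuation route completes after the MTD evaluation period.
- One extra DLT moves the recommendation only from some starting points. With 0/3 at 4 mg and 0/3 at 6 mg, Table 10.2:1 gives these overdose probabilities at 8 mg (an independent grid recalculation with the Table 7.1:2 prior is in parentheses). From 0/3 to 1/3: 0.058 to 0.234 (0.067 to 0.239), 8 mg kept. From 0/6 to 1/6: 0.023 to 0.106 (0.023 to 0.103), 8 mg kept. From 1/6 to 2/6: 0.106 to 0.274 (0.103 to 0.268), which crosses 0.25, and 7 mg is recommended. These figures show what any extra DLT does. They do not measure this ambiguity.

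**Conclusion.** The contradiction is real and should be resolved. At cycle starts with a scheduled eye exam, a low-grade RPED is held under 4.1.4.1 and treated under either table, and the after-visit half of the footnote h window conflicts with the cycle-start check.

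Its size cannot be put in patients, because the documents give no RPED frequency. The consequence is first one of consistent patient management. For the endpoints it is secondary and conditional: the event must be treatment-related, the hold must exceed 4 weeks, and re-exposure must not be agreed. It would then bear mainly on the on-treatment DLT count, the recommended dose and the final model rerun.

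This rests on two assumptions: that a low-grade RPED can be graded 1 under CTCAE version 5, and that a DLT arising through discontinuation is dated to when discontinuation becomes required. No text dates it back to the exam.

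**What to change.** - Reconcile 4.1.4.1 with Tables 4.1.4.2:1 and 4.1.4.2:2 so that one RPED finding leads to one action, and say which table covers RPED.
- Reconcile the exam window in Flow Chart footnote h with the cycle-start eye criterion.
- In 5.2.6.3, make the Grade 2 floor of the Cycle 2 delay clause consistent with the pause and permanent-discontinuation clauses for holds caused only by the eye criterion. State whether the limitation to Cycle 1 applies to the pause.

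Which clinical rule applies is for the sponsor to decide. The cost is wording in a protocol amendment. The SAP takes its DLT definition from protocol 5.2.6.3, so it needs no separate change.
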